4.6.3. Clinical Laboratory Evaluation

All numerical laboratory tests for serum chemistries, fasting lipids, hematology, rheumatoid factor (RF) and anti-CCP antibodies, CRP, and ESR will be summarized by treatment arm for observed and change from baseline values during the Treatment Period.

Urinalysis will appear in data listings.

Summary of B-cells, immunoglobulins (Igs), and immunogenicity tests are described in the subsections below.

Change from baseline in laboratory tests will be summarized for patients who have both a baseline and at least postbaseline result.

Change from the minimum value on or prior to the date of the first injection of study treatment to the minimum value during the Treatment Period in laboratory tests will be summarized for patients who have both a baseline and at least 1 postbaseline result. Similarly, change from the maximum value on or prior to the date of the first injection of study treatment to the maximum value during the Treatment Period in laboratory tests will be summarized for patients who have both a baseline and at least 1 post-baseline result. Scheduled visits, unscheduled visits, and repeat measurements will be included.

The frequency and percentage of patients with treatment-emergent abnormal, high, or low laboratory results at any time will be summarized. Similarly, the frequency and percentage of patients with treatment-emergent abnormal, high, or low laboratory results will be summarized. A treatment-emergent abnormal result is defined as a change from normal at all baseline visits to abnormal at any time during the Treatment Period. A treatment-emergent high result is defined as a change from a value less than or equal to the high limit at all baseline visits to a value greater than the high limit at any time during the Treatment Period. A treatment-emergent low result is defined as a change from a value greater than or equal to the low limit at all baseline visits to a value less than the low limit at any time during the Treatment Period. For each laboratory test, only patients who were normal (that is, less than or equal to the high limit for treatment-emergent high, or greater than or equal to the low limit for treatment-emergent low) at all baseline visits and who have at least 1 nonmissing postbaseline result will be included in the denominator when computing the percentages of patients with treatment-emergent abnormal,

high, or low results. Scheduled visits, unscheduled visits, and repeat measurements will be included. Covance Reference Ranges will be used to define the low and high limits. Listing of significant lab test abnormalities will be provided.

Shifts from baseline to maximum postbaseline result during the Treatment Period for alanine aminotransferase (ALT), aspartate aminotransferase (AST), alkaline phosphatase (ALP) and total bilirubin will be provided for the following categories:

- ALT, AST; \leq 1 × upper limit of normal (ULN), >1 to <3 × ULN, \geq 3 to <5 × ULN, \geq 5 to <10 × ULN, and \geq 10 × ULN
- ALP; $\leq 1 \times ULN$, ≥ 1 to $\leq 1.5 \times ULN$, ≥ 1.5 to $\leq 2 \times ULN$, $\geq 2 \times ULN$
- Total bilirubin; $\le 1 \times ULN$, >1 to $<1.5 \times ULN$, ≥ 1.5 to $<2 \times ULN$, $\ge 2 \times ULN$

Lab Evaluation of Drug-Induced Serious Hepatotoxicity plot will be created with maximum postbaseline ALT/AST divided by ULN vs. maximum postbaseline total bilirubin divided by ULN.

Hematologic changes will be defined based on clinical laboratory assessments. Common Terminology Criteria for Adverse Events (CTCAEs) will be applied for selected laboratory tests. Shifts from maximum baseline to maximum postbaseline result will be provided by treatment periods for the categories in Appendix 11 (Section 6.11).

Shift tables from maximum baseline to maximum postbaseline for lipid effects that include total cholesterol and triglycerides will be categorized based on NCEP levels in Appendix 11 (Section 6.11) and summarized by treatment periods.

Shift table from maximum baseline to maximum postbaseline for renal function that includes elevated creatinine will be categorized based on CTCAE in Appendix 11 (Section 6.11) and summarized by treatment periods.

Scheduled visits, unscheduled visits, and repeat measurements will be included.

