8.2.4. Clinical Safety Laboratory Tests

See Section 10.2, Appendix 2 for the list of clinical laboratory tests to be performed and the SoA for the timing and frequency.

The investigator must review the laboratory results, document this review, and report any clinically relevant changes occurring during the study as an AE. The laboratory results must be retained with source documents unless a Source Document Agreement or comparable document cites an electronic location that accommodates the expected retention duration.

Clinically significant abnormal laboratory findings are those which are not associated with the underlying disease, unless judged by the investigator to be more severe than expected for the participant's condition.

All laboratory tests with values considered clinically significantly abnormal during participation in the study or within approximately 50 days after the last dose of study intervention should be repeated until the values return to normal or baseline or are no longer considered clinically significant by the investigator or medical monitor.

- If such values do not return to normal/baseline within a period of time judged reasonable by the investigator, the etiology should be identified and the sponsor notified.
- All protocol-required laboratory assessments, as defined in Section 10.2, Appendix 2, must be conducted in accordance with the SoA, standard collection requirements, and laboratory manual.

If laboratory values from non-protocol specified laboratory assessments performed at an investigator-designated local laboratory require a change in participant management or are considered clinically significant by the investigator, for example, SAE or AE or dose modification, then report the information as an AE.

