Section 4.6.3	Updated the AST, AST, ALP and Total bilirubin threshold for the shift from baseline analysis	• Correction
Section 4.6.3	Specified the shift from baseline analyses of hematologic changes, lipid effects and renal function are to be performed using maximum baseline and postbaseline results	• Clarification
Section 4.6.4.2	Removed the analyses which are not needed.	• Correction
Section 4.7.1	Clarified the subgroups for the efficacy subgroup analyses	• Clarification
Section 6.2		Clarification
Section 6.8	Removed Italy from the list of geographic region since no subjects from Italy were enrolled.	• Correction

Table KDAF.1.1. SAP Version History Summary

SAP Version	Approval Date	Change	Rationale
1	07 Apr 2023	Not Applicable	Original version
2	29 Nov 2023	See above	Version 2
3	See date on Page 1		

Abbreviation: SAP = statistical analysis plan.

1. Introduction

Study J1A-MC-KDAF (KDAF) is a Phase 2b, double-blind, placebo-controlled study to evaluate peresolimab in adult participants with moderately-to-severely active rheumatoid arthritis (RA).

[figure not shown]
There are no changes to the analyses described in the protocol.

[figure not shown]

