4.1. General Considerations

Statistical analysis of this study will be the responsibility of sponsor or its designee. A detailed SAP describing the statistical methodologies will be developed by the sponsor or its designee.

Handling of missing, unused, and spurious data are addressed prospectively in the overall statistical methods described in the protocol and in the SAP, where appropriate. Adjustments to the planned analyses are described in the final clinical study report (CSR).

Baseline for the Treatment Period is defined as the last nonmissing assessment on or prior to the date of the first injection of study treatment for efficacy, unless otherwise specified. In most cases, this will be the measure recorded at Week 0 (Visit 2). For safety analyses, baseline will be defined by period as last nonmissing assessment prior to the first dosing of each period. The Treatment Period starts after the first injection and ends on date of Visit 18 (Week 60) or early discontinuation (ED). Any assessment collected after the first injection is defined as postbaseline for the Treatment Period. If ET visit does not occur, last injection date will be considered as the end of the treatment period. Baseline for safety analysis of the Posttreatment Follow-Up period (Period 4) is defined as the last nonmissing assessment prior to entering Period 4, that is date of Visit 18 (Week 60) or ET.

During this study, data issue was identified for the collection date/time of the electronic clinical outcome assessments (eCOA). Same analysis visit was assigned to eCOA assessment with different collection date than the corresponding visit date. Because of this, study team came up with a method to handle this data issue, which is the analysis visit numbers for electronic clinical outcome assessments (eCOA) data will be assigned based on the actual visit date recorded in the electronic case report form (eCRF). If the eCOA assessment date is within +/- 3 days window of the actual visit, then the analysis visit number of the eCOA assessment will be assigned as the actual visit number. If the eCOA assessment date is outside +/- 3 days window of all the actual visits, then the analysis visit of the eCOA assessment will be considered as unscheduled visit. The eCOA data will be used for the analysis only when the analysis visit number of the eCOA assessment is identical to the visit number captured in the eCOA system.

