4.6.4.2. Serum Immunoglobulin Levels and Cytokines

Serum Ig levels, including IgA, IgG, and IgM, and cytokines will be summarized by treatment arm for baseline, postbaseline visits, and both change from baseline and percent change from baseline to each postbaseline visit. Baseline is defined as the last nonmissing result on or prior to the date of the first injection of study treatment.

For each parameter, the mean percentage change from baseline over time (in weeks) will be summarized graphically by treatment arm.

Shift tables will be produced showing the frequency and percentage of patients with a minimum postbaseline result during the Treatment Period in each relevant category, by treatment arm and baseline result. Such shift tables will be produced for the following parameters and categories:

- IgA; <LLN to ≥ 0.35 g/L, and <0.35 g/L
- IgG: <LLN to \ge 2.82 g/L, and <2.82 g/L
- IgM: <LLN to \ge 0.20 g/L, and <0.20 g/L

A by-patient listing of serum Ig levels and cytokines during the Treatment Period will be provided.

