6.11. Appendix 11: Common Terminology Criteria for Adverse Events (CTCAE)

Selected Hematologic Events

Event	Laboratory	Grade	Criteria in Système International (SI) Units	Criteria in Conventional (CN) Units
	Test			
Anemia*	Hemoglobin	0 (normal)	≥7.27 mmol (Fe)/L for females and ≥8.18 mmol (Fe)/L for males	≥12 g/dL for females and ≥13.5 g/dL for males
		1	<7.27 mmol (Fe)/L for females and 8.18 mmol (Fe)/L for males and \geq 6.2 mmol (Fe)/L	<12 g/dL for females and 13.5 g/dL for males and $\geq\!10$ g/dL
		2	$<$ 6.2 mmol (Fe)/L and \ge 4.9 mmol (Fe)/L	$<$ 10 g/dL and \ge 8.0 g/dL
		3	<4.9 mmol (Fe)/L and ≥4.0 mmol (Fe)/L	<8.0 g/dL and ≥6.5 g/dL
		4	<4.0 mmol (Fe)/L	<6.5 g/dL
Leukopenia*	White blood cell	0 (normal)	≥4.0 billion cells/L	≥4.0 thousand cells/uL
	(WBC) count	1	<4.0 billion cells/L and ≥3.0 billion cells/L	<4.0 thousand cells/uL and ≥3.0 thousand cells/uL
		2	<3.0 billion cells/L and ≥2.0 billion cells/L	<3.0 thousand cells/uL and ≥2.0 thousand cells/uL
		3	<2.0 billion cells/L and ≥1.0 billion cells/L	<2.0 thousand cells/uL and ≥1.0 thousand cells/uL
		4	<1.0 billion cells/L	<1.0 thousand cells/uL
Neutropenia*	Absolute	0 (normal)	≥2 billion cells/L	≥2 thousand cells/uL
	neutrophil count	1	<2 billion cells/L and ≥1.5 billion cells/L	<2 thousand cells/uL and ≥1.5 thousand cells/uL
	(ANC)	2	<1.5 billion cells/L and ≥1.0 billion cells/L	<1.5 thousand cells/uL and ≥1.0 thousand cells/uL
		3	<1.0 billion cells/L and \geq 0.5 billion cells/L	<1.0 thousand cells/uL and ≥0.5 thousand cells/uL
		4	<0.5 billion cells/L	<0.5 thousand cells/uL
Lymphopenia*	Lymphocyte	0 (normal)	≥1.1 billion cells/L	≥1.1 thousand cells/uL
	count	1	<1.1 billion cells/L and ≥0.8 billion cells/L	<1.1 thousand cells/uL and ≥0.8 thousand cells/uL
		2	< 0.8 billion cells/L and ≥ 0.5 billion cells/L	<0.8 thousand cells/uL and ≥0.5 thousand cells/uL
		3	$<$ 0.5 billion cells/L and \ge 0.2 billion cells/L	<0.5 thousand cells/uL and ≥0.2 thousand cells/uL
		4	<0.2 billion cells/L	<0.2 thousand cells/uL
Thrombocytopenia*	Platelet count	0 (normal)	≥150 billions/L	≥150 thousands/uL
		1	<150 billions/L and ≥75 billions/L	<150 thousands/uL and ≥75 thousands/uL
		2	<75 billions/L and ≥50 billions/L	<75 thousands/uL and ≥50 thousands/uL
		3	<50 billions/L and ≥25 billions/L	<50 thousands/uL and ≥25 thousands/uL
		4	<25 billions/L	<25 thousands/uL

Lipid Effects

Laboratory Test	Grade	Criteria in Système International (SI) Units	Criteria in Conventional (CN) Units

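### The hematology CTCAE shift table uses the highest value for five tests that worsen as they fall, so it shows the mildest grade reached, not the worst

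*SAP*

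**What the plan says.** SAP Section 4.6.3 applies CTCAE grading to selected hematology tests and then sets the rule: "Shifts from maximum baseline to maximum postbaseline result will be provided by treatment periods for the categories in Appendix 11 (Section 6.11". The Version History entry for Section 4.6.3 under SAP Version 3 covers hematology, lipids and renal function together and says that the shift analyses "are to be performed using maximum baseline and postbaseline results". On which results count, Section 4.6.3 adds: "Scheduled visits, unscheduled visits, and repeat measurements will be included".

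The grades are in Appendix 11 (Section 6.11) under "Selected Hematologic Events". The five events there are anemia, leukopenia, neutropenia, lymphopenia and thrombocytopenia.

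Three other places bear on the point:

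- SAP Section 4.1, for safety analyses: "baseline will be defined by period as last nonmissing assessment prior to the first dosing of each period".
- SAP Section 4.6.4.2, where low immunoglobulin is the concern, tabulates "patients with a minimum postbaseline result during the Treatment Period in each relevant category".
- Protocol Section 8.2.4 says that clinically significant abnormal laboratory values "should be repeated until the values return to normal or baseline or are no longer considered clinically significant".

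**The concern.** A CTCAE shift table is meant to show how far participants moved toward a severe grade. For a test that worsens downward, the highest value in the period is the least abnormal one. Combined with the Appendix 11 cutoffs, the maximum rule therefore returns the best grade reached. The rule suits the lipid and creatinine tables, which worsen upward, but it has been carried over to five tests that go the other way.

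Two features of the plan add to the masking. Repeat and unscheduled results enter the table, and clinically significant abnormal values are to be retested. A recovery to normal within the same period then removes the event from the table, and clinically significant falls are the ones most likely to generate recovery values.

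This is the only by-arm cytopenia table in the SAP that uses CTCAE grades.

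**Working it through.** The plan states no figure to reproduce; the check is of the rule itself.

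**Inputs.** Lower bounds of each grade from SAP Appendix 11 (g/dL for hemoglobin, billion/L otherwise). A value below the last bound is Grade 4.

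| Test | Grade 0 | Grade 1 | Grade 2 | Grade 3 |
|---|---|---|---|---|
| Hemoglobin, female | 12 | 10 | 8 | 6.5 |
| Hemoglobin, male | 13.5 | 10 | 8 | 6.5 |
| Leukocytes | 4 | 3 | 2 | 1 |
| Neutrophils | 2 | 1.5 | 1 | 0.5 |
| Lymphocytes | 1.1 | 0.8 | 0.5 | 0.2 |
| Platelets | 150 | 75 | 50 | 25 |

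**Formula.** grade(v) = the number of bounds that v lies below. This never increases as v rises, so grade(highest value) is the lowest grade in the period and grade(lowest value) is the highest. A check on 100,000 simulated sets of 1 to 12 results found no exception. Creatinine served as a control: for 0.9, 1.6 and 6.5 times ULN, the maximum gives Grade 4, which is the worst grade, so the rule works there.

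**Illustrative series.** The values are chosen for illustration; the grading is exact.

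| Test, baseline | Postbaseline values | Maximum rule | Minimum rule |
|---|---|---|---|
| Neutrophils, 3.8 | 3.5, 0.4, 3.6 | 0 to 0 | 0 to 4 |
| Neutrophils, 3.8 | 0.4, 0.9 | 0 to 3 | 0 to 4 |
| Neutrophils, 3.8 | 0.4, 0.9, 1.6 | 0 to 1 | 0 to 4 |
| Neutrophils, 3.8 | 0.4, 0.9, 2.1 | 0 to 0 | 0 to 4 |
| Platelets, 180 | 40, 62 | 0 to 2 | 0 to 3 |
| Platelets, 180 | 40, 62, 155 | 0 to 0 | 0 to 3 |

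In rows 2 to 4, each further recovery value lowers the tabulated grade, although the worst value stays at 0.4.

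**Baseline after Period 2.** Take neutrophils of 3.9 and 3.8 before the first injection; 3.5, 0.4 and 1.2 in Period 2 (1.2 being the Week 12 predose value); and 1.1, 0.8 and 1.3 in Period 3A.

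- Period 2: the maximum rule gives 0 to 0 and the minimum rule 0 to 4.
- Period 3A, maximum rule: the postbaseline value is 1.3, Grade 2. The shift is 2 to 2 if only the value of 1.2 counts as baseline, and 0 to 2 if the maximum reaches back to 3.9. Section 4.6.3 does not say which.
- Period 3A, postbaseline minimum 0.8, Grade 3: the shift is 2 to 3 from the Section 4.1 by-period baseline of 1.2, but 0 to 3 from a pre-first-injection baseline of 3.8.

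The correction therefore has to fix the baseline as well as the direction.

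**The case against.** The best defense is that maximum means maximum grade. The sentence follows the introduction of CTCAE and refers to categories that are grades; on that reading the table is correct. In Appendix 11 all five hematologic events carry an asterisk, the lipid and creatinine rows do not, and no footnote survives in the available text, so a clarifying note cannot be ruled out. The Version 3 log entry uses the same shorthand and is not independent evidence.

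This leaves intent open but does not rescue the wording. Section 4.6.3 says result, the same noun it uses for the liver tests, where it means the laboratory value, and the immunoglobulin shifts ask for the minimum explicitly. A programmer following the sentence would take the highest value.

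The second argument is that little is lost. The change from the baseline minimum "to the minimum value during the Treatment Period in laboratory tests will be summarized", there are treatment-emergent-low percentages and a listing of significant abnormalities, and reported events reach the adverse event table by maximum severity. Cytopenia is not among the SAP's adverse events of special interest. This stands as a limit on the size of the problem, but none of these outputs is CTCAE-graded. Treatment-emergent low also counts only participants at or above the low limit at all baseline visits. Protocol Section 5.1 admits hemoglobin from 10.0 g/dL, neutrophils from 1.5, platelets from 100, leukocytes from 3.0 and lymphocytes above 0.50 (billion/L), which spans Grade 1 and, for lymphocytes, Grade 2. Anyone who enters below the laboratory's low limit and then worsens is outside that summary.

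Third, replacing the maximum baseline with a last value goes beyond correcting direction. Minimum to minimum would also cure the main error, so the baseline choice is secondary.

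**Conclusion.** The concern holds: the rule is wrong as written. For all five hematologic events it tabulates the mildest grade in each period, and one normal value gives Grade 0. The error runs in one direction only, toward under-reporting cytopenia, and in the worked series it turns Grade 4 neutropenia and Grade 3 thrombocytopenia into Grade 0.

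The reach is one descriptive safety table; no efficacy result or test is affected. How many participants would be misplaced cannot be derived from the documents. The conclusion rests on reading result as the laboratory value. If worst grade was intended, the sentence still needs correcting so that it is programmed that way. This should be fixed, but it does not threaten the trial's main conclusions.

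**What to change.** For the five hematologic tests, replace the sentence in SAP Section 4.6.3 with:

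> Shifts from baseline to minimum postbaseline result (worst CTCAE grade) will be provided by treatment period, with baseline defined by period as in Section 4.1.

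Keep maximum to maximum for cholesterol, triglycerides and creatinine. If the sponsor prefers minimum baseline to minimum postbaseline, the text must also state which results form the baseline of each period. In the worked example, a minimum reaching back over all earlier values would pick up 0.4 (Grade 4) and show Period 3A as 4 to 3.

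The cost is one SAP sentence and a program change for five tests: postbaseline maximum to minimum, and baseline taken by period. No new data are needed. If the table has already been produced, rerun it and describe the change in the clinical study report, as Section 4.1 provides for adjustments to planned analyses.

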4.6.4. Pharmacodynamics

4.6.4.1. Flow Cytometry

For flow cytometry panel, the absolute count and relative count (that is, as a percentage of the total lymphocyte population) will be summarized by treatment arm for baseline and all postbaseline visits during the Treatment Period using descriptive statistics.

The change from baseline and the percent change from baseline to each postbaseline visit during the Treatment Period will be summarized for absolute and relative count. Note that the baseline count is defined as the average of the nonmissing results on or prior to the date of the first injection of blinded study treatment, unless 1 is missing, in which case the nonmissing result will be used. Unscheduled and repeated measurements will be included.

In addition, the mean absolute and relative counts during the Treatment Period will be presented graphically over time (in weeks) by treatment arm. Similarly, the mean percentage change from

baseline in absolute and relative counts will be presented graphically over time (in weeks) by treatment arm.

A by-patient listing of cytometry cell counts during the Treatment Period will be provided.

4.6.4.2. Serum Immunoglobulin Levels and Cytokines

Serum Ig levels, including IgA, IgG, and IgM, and cytokines will be summarized by treatment arm for baseline, postbaseline visits, and both change from baseline and percent change from baseline to each postbaseline visit. Baseline is defined as the last nonmissing result on or prior to the date of the first injection of study treatment.

For each parameter, the mean percentage change from baseline over time (in weeks) will be summarized graphically by treatment arm.

Shift tables will be produced showing the frequency and percentage of patients with a minimum postbaseline result during the Treatment Period in each relevant category, by treatment arm and baseline result. Such shift tables will be produced for the following parameters and categories:

- IgA; <LLN to ≥ 0.35 g/L, and <0.35 g/L
- IgG: <LLN to \ge 2.82 g/L, and <2.82 g/L
- IgM: <LLN to \ge 0.20 g/L, and <0.20 g/L

A by-patient listing of serum Ig levels and cytokines during the Treatment Period will be provided.

4.6.4.4. Immunogenicity

A participant is defined as evaluable for TE ADA if the participant has a nonmissing baseline ADA result and at least 1 nonmissing postbaseline ADA result.

A participant who is evaluable for TE ADA is defined as TE ADA+ if either of the following holds:

A NAb+ participant is defined as a TE ADA+ participant where an NAb Present result is detected for at least 1 postbaseline ADA sample.

The frequency and percentage of TE ADA+ and NAb+ patients will be summarized by treatment arm.

The time to the development of TE ADA will be calculated as:

Time to development of TE ADA (in days) = Date of development of TE ADA – Date of first injection + 1.

If a patient has not developed TE ADA, they will be censored at the date of the last immunogenicity assessment during the Treatment Period.

The frequency and percentage of patients with both a TE ADA+ incidence (yes, no) and at least 1 TE hypersensitivity AE (yes, no) will be summarized by treatment arm. Similarly, the frequency and percentage of patients with both a TE ADA+ incidence (yes, no) and at least 1 treatment-emergent injection site reaction (yes, no) AE will be summarized by treatment arm.

